Since all materials used to treat such cases have distinct chemical compositions, they have different properties that affect their clinical outcome. Therefore, it is essential to compare them clinically because any restoration's clinical outcome affects its long-term success. According to the null hypothesis, different materials would not significantly affect the clinical result of ceramic overlay restorations.

Patients in all groups will receive a minimally invasive restoration with high esthetic advantages (Protection of the weak cusps and elimination of carious lesions with an esthetic way out) and long-term success of their affected carious hypomineralized permanent molars (IPS e.max CAD or Direct nanohybrid flowable composite) that require minimal preparation depends on the type of restoration will receive.

Aim of the study:

This randomized controlled trial study will evaluate the clinical success of direct nanohybrid flowable composite versus IPS e.max CAD Partial Coverage.

Research question:

Are the direct nanohybrid flowable composite and IPS e.max CAD Partial Coverage clinically successful materials in restoring the carious Hypomineralized Permanent Molars?

PICOS:

P: Patients suffer from hypomineralized permanent molars

I: Direct nanohybrid flowable composite

C: IPS e.max CAD

O: Clinical Success (aesthetics, functional and biological criteria))

II. Methods

Study Design:

Study design: Randomized Controlled Trial

Estimated Enrolment: 48 Carious Hypomineralized Permanent Molars

Allocation: Randomized

Intervention Model: Parallel Assignment

Primary Purpose: Restorations Hypomineralized Permanent Molars

Official Title: Comparative Clinical Evaluation of Partial Coverage CAD/CAM Restoration Versus Nanohybrid Composite of Carious Hypomineralized Permanent Molars: A Randomized Controlled Trial.

Estimated Study Start Date: December 2023 [Time frame: 12 months] Estimated Primary

Completion Date: January 2025

Trial design:

The study is a randomized controlled trial (RCT) where 2 arm parallel groups with a 1:1 allocation ratio were compared. The child participants and the legal guardian of each participating child and the statistician were blinded.

Outcome Measures:

1. **Primary outcome:** Clinical success [Time Frame: 12 months].

- According to FDI World Dental Federation criteria **[Appendix A]**

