- There were three assessment categories (aesthetics, function, and biological), each with five subcategories. From best to worst, the subcategories were:
(1) clinically excellent, (2) clinically good, (3) clinically sufficient, (4) clinically not sufficient but repairable, and (5) clinically unacceptable. Assessment with category (5) was rated as a clinical failure.
- At the follow-up visits over one year at (baseline “1 day “, 6 and 12 months) after cementation., will take standardized photographs and the restorations will clinically evaluate by an independent and calibrated clinician.

Eligibility Criteria

Ages Eligible for Study: Above 6 Years

Sexes Eligible for Study: All

Accepts Healthy Volunteers: Yes

Criteria

Inclusion Criteria:

1. Above 6 years old
2. Cooperative children with large carious First Permanent Molars (FPM) lesions associated with weak cusps and defected hypo-mineralized enamel.
3. Apparently healthy patients.
4. Patients will be available to be clinically reviewed up to 1 year

Exclusion Criteria:

1. Patients with Symptoms of pulpitis.
2. Patients with uncontrolled active tooth decay or periodontal disease (i.e. 4+ mm probing depth and bleeding on probing).
3. Poor oral hygiene and motivation.
4. Patients with parafunctional habits (e.g., bruxism, biting on hard objects).
5. Patients with debilitating illnesses or complicating medical conditions

Explanation regarding the choice of comparators:

IPS e.max CAD: Till now, glass-ceramic-based restorations still offer the best translucency and esthetic qualities. The novel generation of lithium disilicate-based materials as IPS e.max CAD provides standard thickness and quick fabrication. Moreover, the adhesive technique used with this restoration type significantly raises its mechanical properties. (6)

Beautifil Flow Plus X (Shofu) is a bioactive flowable nano-hybrid restorative with a newly developed patented nanofiller. It is indicated for all classes including occlusal and cusp. It has all the Giomer Technology attributes, anti-bacterial, acid neutralization, and fluoride release and recharge, with improved handling and effortless polishing, and maintains a long-lasting shine. Beautifil Flow Plus X has the strength, durability, and aesthetics of a hybrid composite. (7)

Sample size (Power analysis):

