Sample size calculated depending on a previous study (Alaa M. Eldehna a et al., 2023) as reference. (8) According to this study, the probability of surface gloss as an aesthetics criterion in group 1 is 0.96. If the estimated probability of group 2 is 0.6, we will need to study 20 cases in each group with probability (power) 0.8. The Type I error probability. We used the chi-squared test to evaluate that was performed by using P.S.Power 3.1.6. Total sample size increased to 24 subjects per group to compensate for a 15 % drop out. Sample size calculation was achieved using chi-squared test to evaluate that was performed by using P.S. Power3.1.6, software Version 3.1.2 (Vanderbilt University, Nashville, Tennessee, USA).

Statistical Methods

Statistical analysis:

Data was collected, tabulated, and statistically analyzed using Microsoft Excel ® 2016, Statistical Package for Social Science (SPSS)® Ver. 24. And Minitab ® statistical software Ver. 16.

Handling of numerical / quantitative variables:

Numerical data will be explored for normality by checking the data distribution using Kolmogorov-Smirnov and Shapiro-Wilk tests. Data will be presented as mean & standard deviation. If data will

be normally distributed comparison between 2 different groups will be performed by using independent t-test, comparison between 2 related groups will be performed by using Paired t-test, while comparison between more than 2 groups will be performed by using One Way ANOVA test followed by Tukey's Post Hoc test for multiple comparisons. If data will be non-parametric data comparison between 2 different groups will be performed by using Mann-Whitney test, comparison between 2 related groups will be performed by using Wilcoxon Signed Rank test, while comparison between more than 2 groups will be performed by using Kruskal-Wallis test.

Handling of categorial / qualitative variables:

Data will be presented as frequency and percentages. All comparisons will be performed by using Chi square test.

Recruitment:

The study will be conducted at the pediatric dentistry department of MSA University pediatric outpatients. All subjects will be monitored and reviewed at day 1 after 6 months and 12 months.

Post-trial care

- Oral hygiene instructions and serving brush and toothpaste
- Dietary recommendations

Patients Guardians Consent and Ethical Approval

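### If visits are compared within an arm, as the test list implies, every stated route for three visits ignores that the same molars are re-graded; the cost is lost power, and it is minor

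*Combined protocol and SAP*

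**What the plan says.** - **Visits.** Each restoration is graded on the FDI criteria at baseline (day 1), 6 months and 12 months. Outcome Measures introduces this with "At the follow-up visits over one year at", and Recruitment repeats it: "All subjects will be monitored and reviewed at day 1 after 6 months and 12 months".
- **Design and primary outcome.** There are two parallel arms, 1:1. The primary outcome is "Clinical success [Time Frame: 12 months"], with grades from 1 to 5. On failure: "Assessment with category (5) was rated as a clinical failure".
- **Categorical data** (Handling of categorial / qualitative variables). One rule: "All comparisons will be performed by using Chi square test".
- **Numerical data** (Handling of numerical / quantitative variables). "Numerical data will be explored for normality by checking the data distribution using Kolmogorov-Smirnov and Shapiro-Wilk tests". If normal: independent t for two groups, paired t for two related groups, one-way ANOVA with Tukey for more than two. If not normal: Mann-Whitney for two groups, then "comparison between 2 related groups will be performed by using Wilcoxon Signed Rank test", and "comparison between more than 2 groups will be performed by using Kruskal-Wallis test".

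Friedman, Cochran's Q, McNemar and repeated-measures ANOVA are named nowhere. The plan does not say whether FDI grades count as numerical or categorical.

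**The concern.** The plan respects pairing for two visits of scores, but drops it for three visits and for all categorical data. Chi-square, Kruskal-Wallis and one-way ANOVA treat the 72 grades from 24 molars at three visits (24 × 3) as 72 unrelated molars.

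What is at stake is a within-arm statement about change over the year, such as loss of lustre, staining or marginal breakdown. The research question asks whether both materials are clinically successful, which invites such statements. A test that ignores positive correlation between visits misses real deterioration more often, and its non-significant result may be reported as stability.

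**Working it through.** **1. The plan's own figure, to see whether this point touches it.** Inputs from the sample size section: proportions 0.96 and 0.60, power 0.80, 15% drop-out. The type I error has no value there; 0.05 two-sided is assumed.

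n = [1.960·√(2·0.78·0.22) + 0.842·√(0.96·0.04 + 0.60·0.40)]² / 0.36² = (1.148 + 0.444)² / 0.1296 = 19.6, so 20 per group; 20/0.85 = 23.5, so 24. The stated figures reproduce. They concern two independent arms and do not depend on how visits are compared.

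**2. Which test each visit comparison reaches.**

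| Data | Two visits | Three visits |
|---|---|---|
| Categorical grades | chi-square (unpaired) | chi-square (unpaired) |
| Scores, not normal | Wilcoxon signed-rank (paired) | Kruskal-Wallis (unpaired) |
| Scores, normal | paired t (paired) | one-way ANOVA (unpaired) |

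The gap is the whole three-visit column and the two-visit categorical cell. The ANOVA cell cannot be dismissed. For a single simulated 1-5 item, Shapiro-Wilk rejected normality at one or more visits (or a visit had no variation) in every run. But the plan does not say how items are combined. For a mean of the ten Appendix A items (assumed inter-item correlation 0.3), it did not reject in 74% of runs at 12 months, though in only 11% at day 1.

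**3. Direction of the error.** With equal variance σ² and within-molar correlation ρ, the difference between two visits has variance 2σ²(1 − ρ). An unpaired test works as if it were 2σ². The overstatement is 1/(1 − ρ): 1.43, 2.00 and 3.33 at ρ = 0.3, 0.5 and 0.7. Positive ρ makes the test conservative; negative ρ does the reverse.

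**4. Size.** The documents give no correlation, grade distribution or decline, so all are assumed. A latent normal with equal correlation was cut to day 1 grade shares of 0.70/0.20/0.07/0.02/0.01. The decline was 0.8 SD by 12 months, half of it by 6 months. The share graded excellent then falls from 70% to Φ(0.524 − 0.8) = 39%. There were 24 molars and 2,000 runs per setting (3,000 for Mann-Whitney), tested at two-sided 0.05, with Monte Carlo error about 0.01.

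| Comparison | Test | ρ = 0.3 | 0.5 | 0.7 |
|---|---|---|---|---|
| Three visits, grades | Kruskal-Wallis | 0.52 | 0.51 | 0.49 |
| | Friedman | 0.63 | 0.74 | 0.89 |
| Three visits, excellent or not | chi-square | 0.44 | 0.42 | 0.40 |
| | Cochran's Q | 0.55 | 0.64 | 0.74 |
| Three visits, score-5 failure | chi-square | 0.08 | 0.07 | 0.05 |
| | Cochran's Q | 0.08 | 0.09 | 0.08 |
| Day 1 vs 12 months, grades | chi-square | 0.35 | 0.34 | 0.33 |
| | Mann-Whitney | 0.66 | 0.68 | 0.70 |
| | Wilcoxon signed-rank | 0.73 | 0.82 | 0.94 |
| Day 1 vs 12 months, excellent or not | chi-square | 0.62 | 0.63 | 0.64 |
| | McNemar, asymptotic | 0.63 | 0.71 | 0.82 |
| | McNemar, exact | 0.52 | 0.59 | 0.68 |

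Repeating the three-visit grade and excellent-or-not comparisons with fresh draws moved these figures by at most 0.04. With 20 molars: Kruskal-Wallis 0.42 / 0.41 / 0.38, Friedman 0.50 / 0.64 / 0.83.

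**5. A second scenario.** With 95% excellent at day 1 and a 1.2 SD decline:
- Kruskal-Wallis 0.63 / 0.63 / 0.64 against Friedman 0.68 / 0.76 / 0.87.
- Score-5 failure: chi-square 0.17 / 0.16 / 0.15 against Cochran's Q 0.19 / 0.19 / 0.20.
- Two visits, excellent or not: chi-square 0.77 / 0.78 / 0.79, asymptotic McNemar 0.78 / 0.83 / 0.88, exact McNemar 0.59 / 0.64 / 0.68.

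**6. False positives with no decline, 24 molars, ρ = 0.3 / 0.5 / 0.7.** Kruskal-Wallis 0.032 / 0.010 / 0.006, Friedman 0.054 / 0.042 / 0.052. Three-visit chi-square (excellent or not) 0.036 / 0.014 / 0.007, Cochran's Q 0.058 / 0.042 / 0.050. In a separate run with other grade cut-points, 20 molars and ρ = −0.3, chi-square reached 0.084 and Kruskal-Wallis 0.083.

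**7. Two visits, binary, by hand.** Suppose all 24 molars are excellent at day 1 and 4 have worsened by 12 months. Chi-square = 48·(24·4)²/(24·24·44·4) = 4.36, p = 0.037. Asymptotic McNemar = 4²/4 = 4, p = 0.046. Exact McNemar p = 2·0.5⁴ = 0.125; mid-p = 0.125 − 0.5⁴ = 0.0625. Here chi-square is not the more cautious test.

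**The case against.** The strongest objection is that the premise is inferred. The aim sets one material against the other, the design is two parallel arms, and success is judged at 12 months. No within-arm comparison of visits is an aim, hypothesis or outcome, and the statistical section could be a generic menu of tests. That stands, and it is why the point is conditional. It does not remove the point: with two arms, the clauses for related groups and for more than two groups have no other evident use. If they are boilerplate, they should go.

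It is also fair that part of the ground is covered. Wilcoxon signed-rank or paired t already handles two visits of scores. Of the two-visit gap on full grades, 31 to 37 points come from ignoring grade order (chi-square to Mann-Whitney) and only 7 to 24 from ignoring pairing (Mann-Whitney to signed-rank).

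A reader might infer that ignoring the pairing produces spurious significant changes. The results above do not show this for non-negative correlation; it needs negative correlation, for which the documents give no ground. A reader might equally infer that a paired test always helps. For a binary outcome at two visits, exact McNemar is weaker than chi-square in several of the settings above.

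**Conclusion.** The point holds conditionally and is minor. If visits are compared within an arm, all three stated routes for three visits, and the one for two visits of categorical grades, use tests for independent groups. In the main case the three-visit loss is 11 to 40 points of power for grades (Kruskal-Wallis against Friedman) and 11 to 34 for excellent or not (chi-square against Cochran's Q). In the second scenario the loss for grades is 5 to 23 points. For failure as the plan defines it the gain is 0 to 5 points, and for a binary outcome at two visits a gain is not assured.

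The sizes rest on assumed correlations, grade shares and declines. The direction rests on positive within-molar correlation, which is plausible but not in the documents.

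It would be wrong to conclude that the main result is compromised. For the 12-month comparison between arms, chi-square is an independent-samples test of the right type, and the 20 (24 with drop-out) per group is untouched. Nor do the documents show that the sponsor has committed to within-arm testing.

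**What to change.** State whether visits will be compared within an arm.

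**If they will:**
- Restrict chi-square, Kruskal-Wallis and one-way ANOVA to independent groups.
- Treat the 1-5 FDI grades as ordered. Use Friedman for the three visits with Holm-adjusted pairwise Wilcoxon signed-rank tests, and the already listed Wilcoxon test for day 1 against 12 months.
- For a binary outcome over three visits, use Cochran's Q.
- For a binary outcome at two visits, pre-specify asymptotic or mid-p McNemar, and note that the exact version can have less power than chi-square.
- Use repeated-measures ANOVA only if a combined numerical score passes the normality check.

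**If they will not:** delete the clauses on related groups and on more than two groups.

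The cost is a few lines in the statistical section. Friedman, Cochran's Q and McNemar are available in SPSS, which the plan already uses. No new data are needed and the sample size does not change.

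### The large-sample chi-square test is adequate for the two-by-two design comparison but too conservative for sparse FDI grade tables; the plan should specify an exact p-value there and fix the two-by-two test in advance.

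*Combined protocol and SAP*

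**What the plan says.** The section on categorical variables (Statistical Methods) gives one rule for every comparison: "All comparisons will be performed by using Chi square test". It offers no alternative for small expected counts and does not mention a continuity correction.

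The section Sample size (Power analysis) uses the same family of test: "We used the chi-squared test to evaluate that was performed by using P.S.Power 3.1.6". Its inputs are that "the probability of surface gloss as an aesthetics criterion in group 1 is 0.96" and that "If the estimated probability of group 2 is 0.6, we will need to study 20 cases in each group with probability (power) 0.8". The significance level is left blank; the sentence reads only "The Type I error probability". Enrolment is then raised: "Total sample size increased to 24 subjects per group to compensate for a 15 % drop out". This agrees with the 48 molars under Study Design and with the "2 arm parallel groups with a 1:1 allocation ratio" under Trial design.

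Outcome Measures defines the primary outcome as clinical success by FDI criteria, with only the worst of five grades counted as failure. Appendix A sets out the individual parameters on scores 1 to 5. The plan does not say whether each parameter is compared as a table of grades, as success versus failure, or both.

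**The concern.** The chi-square p-value is a large-sample approximation, and this is a small trial. In the plan's own scenario the expected number of molars without the good result is 4.4 per arm, below the customary limit of 5. A five-grade table with few molars in the worse grades is much sparser.

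Two things are at stake. First, if the approximation is poor in the grade tables, the test may have less power than the data allow. Second, the plan does not say what happens when software warns of low counts, so the analyst may choose between versions of the test after seeing the data. For 0/20 vs 4/20 failures the uncorrected chi-square gives p = 0.035, the continuity-corrected version 0.114 and Fisher's test 0.106. The first two are both chi-square tests, so both satisfy the plan's sentence, yet they lead to opposite conclusions.

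**Working it through.** **Inputs.** From the plan: rates 0.96 and 0.60, 20 per arm, power 0.80, chi-square test, 15% dropout, 24 enrolled per arm. Assumed: two-sided 5%, because no value is given. Also assumed: all grade distributions below, because the plan gives none.

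**1. The plan's figure.** With pooled rate (0.96 + 0.60)/2 = 0.78, the uncorrected formula is

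n = [1.960·√(2·0.78·0.22) + 0.842·√(0.96·0.04 + 0.60·0.40)]² / (0.96 − 0.60)² = 19.56, so 20 per arm.

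Then 20/0.85 = 23.5, so 24 enrolled. The plan reproduces. With a continuity correction n would be 25, so the sample size rests on the uncorrected test at this level.

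**2. Expected counts, two-by-two.** 20 × 0.22 = 4.4 per arm; with all 24 retained, 24 × 0.22 = 5.28.

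**3. Exact size and power, two-by-two.** Every pair of binomial counts was enumerated; size is at a common rate of 0.78 and power is at 0.96 vs 0.60.

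| Test, 20 per arm | Size at 0.78 | Maximum size | Power |
|---|---|---|---|
| Chi-square, uncorrected | 5.05% | 5.3% | 85.9% |
| Chi-square, continuity-corrected | 2.0% | 2.2% | 73.1% |
| Fisher, two-sided | 2.3% | 2.5% | 76.5% |

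At 24 per arm the uncorrected test has a maximum size of 6.0%, but this occurs at a common rate of 0.50, where expected counts are 12. It is not an effect of sparse cells.

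**4. Rare failures, two-by-two.** At a common failure rate of 5% and 20 per arm, the uncorrected test has a size of 1.2%; at 4% it is 0.7%. It is conservative here, but exact alternatives are more so: Fisher's size at 4% is 0.09%, and Boschloo's at 5% is 0.2%.

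**5. Grade tables.** Take an assumed five-grade distribution of 0.60/0.25/0.10/0.04/0.01 in both arms. Expected counts with 20 per arm are 20 × each probability: 12, 5, 2, 0.8 and 0.2. Three of the five columns fall below 5 and two fall below 1. In 200,000 simulated trials the large-sample chi-square rejected in 2.9%, not 5%.

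Across the four- and five-grade settings examined:

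| p-value for the same statistic | True size |
|---|---|
| Large-sample | 1.8% to 3.8% |
| Exact (permutation) | 3.8% to 4.7% |

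In one assumed five-grade alternative, power was 42% with the large-sample p-value and 53% with the exact one, a difference of 11 points. With three grades and rare worse grades, the two hardly differ.

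**6. How often the two-by-two choice arises.** Under 0.96 vs 0.60, an expected count falls below 5 in 62% of trials at 20 per arm and in 35% at 24 per arm. In 9.4% of trials at 20 per arm the uncorrected chi-square is significant and Fisher is not.

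**The case against.** A reader might infer from the expected count of 4.4 that the error rate in the design comparison is wrong. It is not: the exact size there is 5.05%. The limit of 5 is a rule of thumb. Where two-by-two cells are truly sparse, the test errs on the safe side.

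A reader might also infer that the stated 80% power is lost once the analyst turns to Fisher. The plan's test delivers 86%. Fisher falls short at 20/20 (76.5%) and 21/21 (79.3%), but not at 22/22 (81.8%) or 24/24 (86.2%). The planned dropout leaves 48 × 0.85 = 40.8, about 41 molars. Fisher has 80.2% or 85.0% at 20/21, and 81.6% or 81.1% at 19/22, depending on which arm is larger. Using Fisher only when an expected count is below 5 gives 79.7% at 20/20.

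Nor do the figures support replacing the two-by-two test with Boschloo's. Its power is 84.2% at 20/20, but at 20/21 it can lose 7.5 points against chi-square (80.2% against 87.7%). It also leaves 0/20 vs 4/20 non-significant.

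Against the narrower point, two objections carry weight. The grade distributions are assumed, so the size of the gain is illustrative. And a conservative test does not raise false positives. Both stand, and they limit the point to lost power. A third objection is that FDI scores might be handled under the numerical section by Mann-Whitney. The plan does not say so; if that is intended, the grade-table point would not apply to those analyses.

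**Conclusion.** The point holds in a limited form. For two-by-two comparisons in the design scenario, neither the error rate nor the 80% power is shown to fail. For FDI tables of four or five grades, the large-sample p-value is too conservative at this sample size: about 1.8% to 3.8% true size, with a loss of 11 points of power in one illustration. Those ranges describe the assumed settings examined and are not bounds; the gain shrinks as fewer grades are occupied. The conclusion rests on a two-sided 5% level, about 20 evaluable molars per arm, and FDI grades being compared as categorical tables.

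Separately, the version of the two-by-two test is unstated, and the choice can change a result. That is a gap in pre-specification and needs no assumption about grades.

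**What to change.** In the section on categorical variables, replace the single sentence with two rules, both applied whatever the expected counts:

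- FDI tables with more than two grades use the exact (permutation) p-value of the chi-square statistic.
- Two-by-two comparisons, including 12-month clinical success, use the chi-square test without continuity correction, the version that reproduces the sample size.

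The 20 evaluable and 24 enrolled per arm need not change. The significance level and sidedness should be filled in under Sample size (Power analysis), since the figures here assume two-sided 5%.

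The cost is two sentences, a little more computation and possibly software beyond the packages named. The accepted drawback is that the uncorrected two-by-two test stays conservative when failures are rare (1.2% at a 5% failure rate) and can slightly exceed 5% elsewhere (maximum 5.3% at 20 per arm, 6.0% at 24).
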